The likelihood ratio of a positive and a negative result for ultrasonography were 10.74 and 0.03 respectively, and that for capnography were infinity and 0.04 respectively.

The kappa value was 0.749 (95% CI: 0.567 – 0.931) which meant a good degree of agreement of result between these two methods.

The average time taken for confirmation of endotracheal tube by ultrasonography and capnography were 26.79 ± 7.64 seconds and 43.03 ± 8.71 seconds (mean \pm standard deviation) respectively. The median time for confirmation was 26 seconds with interquartile range [15 - 37] seconds for ultrasonography and 42 seconds with interquartile range [29 - 55] seconds for capnography. Ultrasonography was found to be faster than capnography by 16.36 ± 3.23 seconds (mean \pm standard deviation) and the difference in time was significant ($p = 0.011$).

Conclusion:

Ultrasonography and waveform capnography are both reliable and accurate methods of confirming endotracheal tube position. The use of ultrasound with capnography will help reduce time and increase precision of confirming endotracheal tube position. Ultrasound can confirm endotracheal tube position before manual bag ventilations, and thus may prevent aspiration of gastric contents into patient's lungs.

Keywords: Endotracheal intubation; ultrasonography; capnography.

TABLE OF CONTENTS

Serial No.	Contents	Page No.
1	Introduction	7
2	Literature Review	19
3	Objectives	30
4	Hypothesis	31
5	Methodology	32
6	Results	45
7	Discussion	55
8	Limitations	68
9	Conclusion	69
10	Recommendations	70
11	References	71
12	Appendices	
	Appendix A - PAC Form	77
	Appendix B - Consent	79
	Appendix B – Proforma	80
	Appendix D – Thesis approval letter from IRB	82

LIST OF ABBREVIATIONS

%	Percentage
>	Greater than
<	Lesser than
±	Plus– Minus
α	Alpha
ACLS	Advanced Cardiac Life Support
AHA	American Heart Association
ASA	American Society of Anesthesiologists
β	Beta
BMI	Body Mass Index
BPM	Beats Per Minute
CI	Confidence Interval
CL	Cormack Lange
CO ₂	Carbon Dioxide
COPD	Chronic Obstructive Pulmonary Disease
CPR	Cardiopulmonary Resuscitation
DLT	Double-Lumen Tube
ECG	Electrocardiogram
Eg	Example
ET	Endotracheal
ETCO ₂	End Tidal CO ₂
NIBP	Non-Invasive Blood Pressure
IRB	Institutional Review Board

IOM	Institute of Medicine
IQR	Interquartile Range
κ	Kappa value
Kg	kilogram
LMA	Laryngeal Mask Airway
LR ⁺	Likelihood ratio of a positive test
LR ⁻	Likelihood ratio of a negative test
MCVTC	Manmohan Cardiothoracic Vascular and Transplant Center

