Both capnography and ultrasound are safe and have been shown to be reliable methods of endotracheal tube confirmation in previous studies which will be detailed further in literature review section. Physicians with basic knowledge about these methods can use them in operating rooms and also in emergency rooms and wards. Ultrasound machines are now gaining popularity and their access extends from operation theatres, emergency rooms and even many primary health centres in Nepal.

Conducting this study will help us to see if ultrasound when used along with capnography can reduce time taken and increase precision for endotracheal tube confirmation inside operating theatres; and further advocate use of ultrasound imaging prior to manual ventilation for endotracheal tube confirmation in full stomach or patients at risk of aspiration.

LITERATURE REVIEW

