< 0.1	Large change in likelihood (or in other words high probability of any individual having a negative result on using the diagnostic test).
0.1 – 0.2	Moderate change in likelihood.
0.2 – 0.5	Small change in likelihood.
1	No change.

Data collection and management

The Pre-anaesthetic (PAC) form of the Department of Anaesthesiology, MMC, IOM; (Appendix A) was used to evaluate patients for inclusion into the study. All participants' data such as gender, age, ethnicity, diagnosis, BMI, weight, ASA status, medical comorbidities, airway examination was collected on data entry proforma sheet (Appendix C). The proforma sheet also recorded the baseline vitals and the vitals after induction of anaesthesia and after intubation. The results for ultrasonography and capnography, the respective time taken to obtain the results were recorded in the proforma sheet.

Data entry was done into Microsoft excel 2010. (Appendix E)

Statistical Analysis

Descriptive variables were expressed as mean \pm standard deviation, median, range, interquartile range, frequency, percentage and proportion. The calculations were done in Microsoft excel 2010.

The sensitivity, specificity, positive and negative predictive values, accuracy, along with their confidence intervals and likelihood ratios for positive and negative results were calculated by defining the respective mathematical functions into Microsoft excel 2010.

The mean and median times along with the interquartile range and standard deviations, taken for confirmation by capnography and ultrasonography were calculated using SPSS 23.0. Difference in time was calculated as method 1 (ultrasonography) minus method 2 (capnography) and reported as mean with 95% confidence interval; the results were compared using paired student t-test with p values at 95 % level of significance. The analysis was done using SPSS 23.0.

Kappa statistic was used to see agreement over and above that which would have occurred just by chance between these two methods. The kappa (κ) value was calculated using SPSS 23.0. It was interpreted based on the following criteria³⁸:

Table 4. Interpretation of kappa value.³⁸

Kappa value (κ)	Degree of agreement
0.81 - 1.00	Very good.
0.61 - 0.80	Good.
0.41 - 0.60	Moderate.
0.21 - 0.40	Fair.
<0.20	Poor.

[figure not shown]

Fig. 8. Study flow diagram.

(TP=True Positive, FP=False Positive, TN=True Negative, FN=False Negative)

RESULTS

Descriptive data

Demography

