Both ultrasonography and waveform capnography were found to be good, reliable and fairly accurate diagnostic methods of confirming endotracheal tube position. Ultrasonography was comparable diagnostically with capnography for endotracheal tube confirmation. The comparisons of the pretest and posttest probabilities of the two methods are shown in table 10.

Table 10. Comparison of the diagnostic characteristics of ultrasonography and waveform capnography.

	Ultrasonography	Waveform Capnography
Sensitivity in % (95% CI)	97.62 (91.66- 99.71)	96.43 (89.92 - 99.26)
Specificity in % (95% CI)	90.91 (58.72 - 99.77)	100 (71.51 - 100)
PPV in % (95% CI)	98.80 (92.67- 99.81)	100 (100 – 100)
NPV in % (95% CI)	83.33 (55.66 - 95.22)	78.57 (54.69 - 91.76)
Accuracy in % (95% CI)	96.84 (92.92 - 100)	96.84 (92.92 - 100)
Positive likelihood ratio	10.74	Infinity
Negative likelihood ratio	0.03	0.04

(CI= Confidence Interval, PPV= Positive Predictive Value, NPV= Negative Predictive Value)

Both ultrasonography and capnography together had correctly identified 10 out of the 11 oesophageal intubations. The 84 tracheal intubations were correctly identified by both ultrasonography and capnography or either one of these methods. Using the same formula (page 35), the combined accuracy of both the methods together was 98.94% (94 divided by 95, in percentage).

The analysis of agreement between the ultrasonography and capnography results was done using Cohen's kappa statistics. A kappa value of 0.749 with 95% confidence interval of (0.567 – 0.931) and standard error of 0.093 was found. The kappa value therefore showed a good agreement between the result of these two methods.

Time taken for endotracheal tube confirmation

Real-time ultrasonography was faster than waveform capnography for endotracheal tube confirmation in all cases. The mean time for confirmation by ultrasonography was 26.79 ± 7.64 seconds (mean \pm standard deviation). The mean time for confirmation by capnography was 43.03 ± 8.71 seconds.

The mean difference in time was 16.36 seconds (95% CI: 15.70sec – 17.02 sec). The median difference in time was 16 seconds. The standard deviation in difference in time was 3.23 seconds. The standard error of mean (SEM) was 0.332 seconds. The difference in time was highly significant ($p = 0.011$).

Table 11. Time taken for endotracheal tube confirmation.

	Range (in seconds)	Mean \pm SD (in seconds)	Median (in seconds)	IQR (in seconds)	p-value

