This study used both sidestream and mainstream capnographs. This was because of availability of different types of capnograph at the study sites. The details of sampling line delay are discussed later.

Ultrasonography vs Capnography

Both ultrasonography and waveform capnography were found to be good, reliable and fairly accurate diagnostic methods of confirming endotracheal tube position. Though ultrasonography and capnography were equally sensitive and capnography seemed more specific; the sensitivity, specificity, PPV, NPV of ultrasonography were comparable (statistically not different as seen by their confidence intervals) to waveform capnography.

The combination of ultrasonography and capnography increased precision (accuracy) over using either one of them in this study. Since the studies done previously had compared ultrasonography against capnography as the standard and thus calculated the sensitivity, specificity, PPV, NPV of ultrasound; these were not able to show if ultrasound had increased accuracy over using capnography alone.

Both of these methods are now known to be equally reliable. Hence in case of unmatched result given by these two methods in a patient, a third highly reliable method of confirmation has to be used because both ultrasonography and capnography have statistically not different false positive (1 – specificity) and false negative (1 – sensitivity) rates.

There was generally good agreement between the results produced by ultrasonography and capnography as shown by the kappa value of 0.749 with 95% confidence interval of (0.567 – 0.931). Other studies have shown a good or a very good agreement of these two methods by kappa statistics. The kappa value calculated by Adi et al³⁰, Chou et al²⁸, Karacebay et al²⁷ and Chintamani et al³⁴ were 0.85, 0.93 (0.84 – 1.00), 0.85 and 0.76 respectively.

Real-time, transtracheal, transverse suprasternal ultrasonography was significantly faster ($p = 0.011$) than capnography by 16.36 ± 3.23 seconds (mean \pm SD) in confirming endotracheal tube position in this study. The subgroup analysis between mainstream and sidestream capnographs also showed that the type of waveform capnograph device used did not affect the significant difference in time of ultrasound over capnograph in confirming endotracheal tube position.

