The sidestream capnograph at MCVTC had system response time of < 4 seconds, and that at TUTH had system response time of < 3 seconds. Adjusting for rise time of 200 milliseconds (the actual rise time of sidestream capnograph device used at TUTH; the rise time of that used at MCVTC was unknown), the transit time (delay time) would be in between 3 to 4 seconds in MCVTC sidestream capnograph and in between 2 to 3 seconds in TUTH sidestream capnograph. No delay was expected in mainstream capnograph device.

The median time taken for endotracheal tube confirmation by mainstream capnograph was 37 seconds and that by sidestream capnograph was 45.5 seconds. The combined median time taken for endotracheal tube confirmation by capnography was 42 seconds. The difference in time with ultrasonography was maximum of 19 seconds and minimum of 9 seconds while using mainstream capnograph, and maximum of 24 seconds and minimum of 12 seconds while using sidestream capnograph. These findings correlate to the delay time of sidestream capnographs as mentioned previously. Though theoretically the delay time should not have exceeded 4 seconds, the difference in median time for confirmation between these types of capnographs was 8.5 seconds. The median time for confirmation of endotracheal tube position in this study would be affected by the time taken by the anaesthesia resident for intubation. Thus difference in time for confirmation between the two types of capnographs could be greater or lesser than 8.5 seconds depending on the variability of time taken for intubation in this study.

Few studies have compared if ultrasound can be faster than capnography. Karacebay et al²⁷ found that dynamic transtracheal ultrasound at suprasternal level combined with lung sliding done by two separate operators simultaneously during intubation, was faster in average by 5.9 seconds than capnography for endotracheal tube confirmation. Pfeiffer et al³¹ found that lung ultrasound was in average 7.1 seconds faster than capnography in confirming endotracheal tube position.

The difference in time was greater in this study, likely due to use of sidestream capnograph. But as discussed earlier, this did not affect the significance in difference in time.

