Chintamani et al³⁴ in their study comparing ultrasound and capnography found mean \pm SD time for confirmation by ultrasound to be 12 ± 1.31 secs, and that by capnography to be 8.98 ± 1.04 secs. Their finding of capnography being significantly faster is debatable because they used transtracheal ultrasound at suprasternal level first in transverse view then in longitudinal view, followed also by scanning towards the left side of neck to align the area of oesophagus towards the center of probe. They also have not mentioned the criterion for capnography, whether $ETCO_2$ values were used or not, and the number of waves they counted for a result.

LIMITATIONS

1. This study used both sidestream and mainstream capnographs as per availability at the study sites. Sidestream capnographs have a delay time in reading exhaled CO₂, which does not occur in mainstream capnographs.
2. Different persons (anaesthesia faculties with training in airway ultrasound) performed ultrasound imaging in this study.
3. This study did not see if novice ultrasound operators could also confirm endotracheal tube position by ultrasound imaging earlier than capnography.

CONCLUSION

Ultrasonography and waveform capnography are equally reliable and accurate methods of confirming endotracheal tube position. Confirmation of endotracheal tube position by real-time ultrasonography is faster than capnography independent of the ultrasound operator. The combination of ultrasonography with capnography in practice will help reduce time and increase precision of confirming endotracheal tube position.

RECOMMENDATIONS

- Real-time transtracheal ultrasonography is safe and can be used as an alternate method of confirming endotracheal tube position in operating theatres.
- Using real-time transtracheal ultrasound can help confirm endotracheal tube position earlier than capnography.
- Using real-time transtracheal ultrasound will help avoid manual bag ventilations to confirm endotracheal tube position and can prevent aspiration of gastric contents into lungs in cases of oesophageal intubation.

REFERENCES

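### The claim that combining ultrasound with capnography reduces time rests on no analysis of the combination, and its size, from none to about 14 s, depends on a decision rule the report does not state consistently

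*Combined protocol and SAP*

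**What the plan says.** All references are to the combined protocol and SAP.

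- **Rationale.** The study is meant to "see if ultrasound when used along with capnography can reduce time taken and increase precision".
- **Objectives and Hypothesis.** These cover the time taken by each method and whether ultrasound is the faster of the two. A time for the combination is not listed.
- **Statistical Analysis.** The time contrast is ultrasound minus capnography within patient, tested with a paired t-test. No variable is defined for the two methods used together.
- **Results, time taken.** "Real-time ultrasonography was faster than waveform capnography for endotracheal tube confirmation in all cases". Table 11 gives means of 26.79 s and 43.03 s, and differences between 9 and 24 s.
- **Results, combined accuracy.** The only combined figure is accuracy, 94 of 95. It counts a tracheal tube as correctly identified if at least one method called it tracheal.
- **Discussion, Ultrasonography vs Capnography.** "in case of unmatched result given by these two methods in a patient, a third highly reliable method of confirmation has to be used".
- **Conclusion and Abstract.** The Conclusion says "The combination of ultrasonography with capnography in practice will help reduce time and increase precision of confirming endotracheal tube position"; the Abstract says "The use of ultrasound with capnography will help reduce time".

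**The concern.** The Rationale asks about ultrasound added to capnography, and the Conclusion answers yes on time. The evidence behind that answer is a comparison of ultrasound with capnography. A 16.36 s lead for one method over the other is what would be gained by replacing capnography. It equals the gain from adding ultrasound only if every ultrasound call is acted on without waiting for capnography.

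The gain from combining depends on what is done with each pair of results, and the report points in two directions. The 94/95 accuracy implies a tracheal verdict when either method is positive. The Discussion remark means that both results must be known before they can be called matched or unmatched. Time and accuracy move together under any such rule, so a time benefit taken from one rule cannot be set beside an accuracy figure, or a safeguard, taken from another. What is at stake is whether an oesophageal tube is accepted as tracheal, so a reader needs the time gain and the error count side by side.

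**Working it through.** **1. The report's own figure.** Inputs from Results: mean difference 16.36 s, SD 3.23 s, n = 95. SEM = 3.23/√95 = 0.331 s (stated 0.332). The 95% CI is 16.36 ± t(0.975; 94) × 0.331 = 15.70 to 17.02 s, as stated. The subgroup means in Table 12 agree: (37 × 14 + 58 × 17.87)/95 = 16.36 s. The figure stands as a contrast between single methods. (The stated means differ by 43.03 − 26.79 = 16.24 s; using that value changes nothing below by more than about 0.1 s.)

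**2. Cross-classification of the two calls.** Table 8: ultrasound had 2 false negatives and 1 false positive. Table 9: capnography had 3 false negatives and no false positive. Results says every one of the 84 tracheal tubes was identified by at least one method, so the false negatives do not overlap.
- Both tracheal: 84 − 2 − 3 = 79
- Ultrasound tracheal, capnography oesophageal: 3 + 1 = 4
- Ultrasound oesophageal, capnography tracheal: 2
- Both oesophageal: 10

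Discordant: 4 + 2 = 6 of 95 (6.3%). Kappa from this table is 0.733 against the stated 0.749. One or two overlapping false negatives would give 0.822 or 0.911, so no overlap is the closest fit.

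**3. Time to decision under three readings.** These are used only to show how the answer depends on the rule; none is proposed for practice.

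*(a) Both results awaited, third method if unmatched (Discussion remark).* T = max(T_ultrasound, T_capnography). The differences were "maximum of 19 seconds and minimum of 9 seconds while using mainstream capnograph" and 12 to 24 s with sidestream, all with capnography later. So T = T_capnography in 95/95: mean 43.03 s, 0 s saved. The 6 discordant patients need further time. That time was not recorded; if it is assumed to be 15 to 60 s, the average addition is 6/95 × 15 = 0.9 s to 6/95 × 60 = 3.8 s per patient.

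*(b) Ultrasound tracheal call accepted at once, otherwise wait for capnography (consistent with the 94/95 figure).* 83 patients stop at ultrasound time and 12 wait. Assuming the mean lead applies equally across patients, the saving is 83/95 × 16.36 = 14.3 s and mean time is 43.03 − 14.3 = 28.7 s. Without that assumption, the 12 who wait have leads between 9 and 24 s, so the saving lies between (95 × 16.36 − 12 × 24)/95 = 13.3 s and (95 × 16.36 − 12 × 9)/95 = 15.2 s. Accuracy is 94/95.

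*(c) Only ultrasound oesophageal calls acted on early, tracheal calls wait for capnography.* 12 patients are affected, 10 correctly and 2 as false alarms. Saving: 12/95 × 16.36 = 2.1 s (range 12 × 9/95 = 1.1 s to 12 × 24/95 = 3.0 s). If capnography's call is then final for the other 83, correct calls are 10 + 79 + 1 = 90 of 95 (94.7%), below the 92/95 (96.84%) of either method alone.

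| Reading | Mean saving vs capnography alone | Oesophageal tubes accepted as tracheal | Correct calls |
|---|---|---|---|
| (a) | 0 s, plus unrecorded time in 6 | depends on third method in 1 patient | 89/89 when concordant; 6 to third method |
| (b) | about 14.3 s | 1 of 11 | 94/95 |
| (c) | about 2.1 s | 0 of 11 | 90/95 |
| Capnography alone | reference | 0 of 11 | 92/95 |

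**The case against.** **Reducing time may only mean that ultrasound reads first.** The data support that statement. But the Conclusion already makes it in the sentence before, and then makes a separate claim about the combination in practice.

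**Combined time was not an objective or hypothesis.** Correct. The hypothesis is that ultrasound is the faster method, and the results support its direction. That limits the weight of the point but does not supply the missing analysis for a claim made in both the Abstract and the Conclusion.

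**The third-method sentence is a Discussion remark, not a rule set in the Methodology.** This stands. A reader might infer that the study shows the combination saves no time at all. The documents do not support that: zero saving follows only if both results are awaited, and the Methodology fixes no such rule. The Literature Review also cites a recommendation to use ultrasound as a preliminary test before capnography, which is a different reading of combined use.

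**A saving need not mean accepting a missed oesophageal tube.** This also stands. A reader might infer that any rule that saves time must accept ultrasound's one false positive. Reading (c) shows otherwise, and earlier recognition of oesophageal placement is the benefit the Introduction stresses. The average gain is then small, although it falls mainly on oesophageal tubes: 10 of 11 were flagged 9 to 24 s sooner.

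**The one miss is not hidden.** Results reports that both methods together identified 10 of 11, and the 94/95 counts the miss as an error. What is absent is any link between that error and the time claim.

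**Conclusion.** The claim that the combination reduces time is not supported by any analysis in the report. The 16.36 s difference reproduces but measures one method against the other. Under the readings the documents allow, the average saving over capnography alone runs from 0 s through about 2.1 s to about 14.3 s, and the largest comes with 1 of 11 oesophageal tubes accepted as tracheal against 0 of 11. The combined accuracy of 94/95 belongs to the reading with the largest saving and conflicts with the Discussion remark on unmatched results.

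The zero in reading (a) and the six discordant pairs follow directly from the reported results. The 14.3 s and 2.1 s assume an equal lead across patients; bounds without that assumption are 13.3 to 15.2 s and 1.1 to 3.0 s. The finding that ultrasound gave the earlier result in every patient is unaffected.

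**What to change.** - Reconcile the combined-accuracy paragraph in Results, the Discussion remark on unmatched results, and the Conclusion, so that one meaning of combined use runs through all three. Which rule is appropriate is for the investigators to settle.
- In the Abstract and the Conclusion, limit the time claim to this: ultrasound gave an earlier result than capnography.
- If a claim about combined time is kept, state the rule it assumes. Under that same rule, report from each patient's recorded times and results the time to decision, the accuracy, and the number of oesophageal tubes accepted as tracheal, all against capnography alone.
- State that third-method time was not recorded. The proforma in Appendix C has time fields for ultrasound and capnography only, so time to final resolution in the discordant patients cannot be computed.

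The cost is a change of wording in two places and, if the claim is kept, one derived time per patient from data already held. The downside is a less favourable conclusion.
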